6.1 Eligibility

Eligible participants include women presenting with their infants at one of the 7 chosen CHC sites for their first WBV (typically 3-5 days after delivery).

6.1.1 Inclusion Criteria

- Women bringing infant for their first WBV at chosen CHC

6.1.2 Exclusion Criteria

- PP tubal ligation
- Emergency hysterectomy due to life threatening bleeding during the delivery

6.1.3 Excluded or Vulnerable Populations

Any males will be excluded from the study because the study outcomes of contraceptive method use and pregnancy status are not applicable to males.

6.2 Outcome Variables

Primary outcome:

- **Receipt of all methods of contraception by two months PP.** Using de-identified patient-level EHRS data for eligible women at each clinic within each time interval, we will create a dichotomous variable for receiving any contraception by two months PP. We will work with AllianceChicago's IT team to restrict the data pull to eligible women who attended an infant 3-5 day WBV after the study period began.

Secondary outcome:

- **Receipt of all methods of contraception by six months PP.** This outcome will be calculated similar to the primary outcome with the exception of time-period.
- **Short IPI pregnancies.** During the baseline period (control condition) and 18 months after the introduction of the intervention in each CHC, we will use EHRS data to estimate the clinic-level rate of incoming prenatal patients presenting with a short IPI.

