6.0 Aim 2 Research Design, Methods, and Data Analysis

Aim 2 is to implement linked PP contraception and newborn care in 7 CHCs and evaluate the effect on provision of PP contraception and rates of short-interval pregnancy. We hypothesize that a linked PP contraception care with newborn care model can be implemented successfully in urban and rural CHC settings. PP women offered contraceptive care linked with newborn care would be more likely to receive any form of contraception at two months PP and by six months PP. Additionally, we hypothesize that CHCs will have a lower rate of short IPIs among incoming prenatal patients after implementing the linked contraception care with newborn care model compared with their rate prior to implementation.

Using a novel approach, we will test a patient-oriented alternative delivery system for PP contraception that will fill a gap in our current system resulting in improved contraceptive access for women. We will use a cluster randomized cross-sectional stepped wedge design to test the novel linked contraception and WBV model's impact on increasing PP contraception uptake in urban and rural CHCs, compared to usual care. We will include the 7 CHCs (six urban, one rural) recruited through Aim 1 of this project.

During the intervention period, staff will capture women during the first WBV (typically 3-5 days after delivery) and offer to have the next visit co-scheduled for infant and contraception care. Current practice at all AllianceChicago CHCs is to ensure all newborn infants leave the clinic with the next visit already scheduled. Appointments are scheduled during the discharge process at the end of each visit. During the discharge process all women 0-6 months postpartum who are established patients will be identified by an electronic prompt in the infant's electronic medical record. The prompt will instruct staff to offer the mother a co-scheduled visit for newborn and contraceptive care at the time of the next newborn visit.

Those who agree will be co-scheduled and those who are not in need of care, or do not wish for co-scheduled care, can decline. Women will be excluded if they had a tubal ligation or a long acting reversible contraception planned immediately after delivery. Women will be offered this co-scheduling option at each WBV through six months PP. Repeat opportunities for co-scheduled care are important as women's needs and

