We will conduct a cluster randomized, cross-sectional stepped wedge study to roll out the intervention across sites and assess the change in clinical and implementation outcomes from before to after the adapted intervention is introduced into clinics. The cluster, or unit of analysis, is the clinic (not individual), which is critical for a system-level intervention. In a stepped wedge study, the design is extended so that every cluster provides before and after observations and every cluster switches from the control (usual care) to the intervention condition (linked care) at regular intervals ("steps"), at different points in time. The order in which a cluster switches from control to intervention is randomized. The advantages of the stepped wedge design are that it provides a pragmatic and robust approach to testing the effectiveness of health service delivery interventions (53). The stepped wedge design is pragmatic because the intervention can be rolled out over time. Additionally, no individual patient consent is required for this system-level health service delivery intervention, and therefore outcomes may be obtained through routinely collected de-identified data from the common AllianceChicago EHR. It is a robust design because each cluster provides data under both the control and intervention condition and therefore may serve as its own control, improving the precision of the study. A limitation of the stepped wedge design is the confounding effect of time given that clusters switch over to the intervention at different times. To help control for the effect of time, 4 additional clusters will be randomized to either the control or the intervention for the entire study period, as in a traditional parallel cluster randomized trial.

One urban and one rural CHC site will be randomized to each step occurring at 3-month intervals. Each step includes a 3-month transition period when the individual clinics will prepare to implement linked care. The design is cross-sectional because outcomes are obtained from the subset of patients seen during each time period at each clinic rather than following individually recruited patients over time.

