6.4 Data Analysis

Drs. [name] and [name], our epidemiology and biostatistics experts will conduct all analysis. They will compare the distribution of patient characteristics between the unexposed observations from the control period and the exposed observations during the intervention period, which are analogous to distributions across arms in a parallel cluster randomized trial. Then, they will plot rates of our outcomes over each three- month time period, comparing how rates differ from the control period to the intervention period overall, within each clinic, and between urban and rural clinics to examine the effects of the intervention, time and level of urbanicity on the outcomes. To examine treatment effects for our primary and secondary outcomes related to receipt of all methods of contraception, we will use a generalized linear mixed model, adjusting for the confounding effect of time with the random effect for CHC site and fixed effect for each time interval.⁵³

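### Short inter-pregnancy interval is planned as an unadjusted before/after clinic rate; the time-adjusted model covers only the contraception outcomes

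*Combined protocol and SAP*

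**What the plan says.** Section 6.2 lists short IPI (conception within 18 months of a prior delivery) as a secondary outcome. It is measured in the baseline control period, then later: "18 months after the introduction of the intervention in each CHC, we will use EHRS data to estimate the clinic-level rate of incoming prenatal patients" (those with a short interval). This can mean a reading at month 18 (time point) or over the 18 months after go-live (window). Section 6.0 states the contrast: a lower rate after implementation, "compared with their rate prior to implementation". Section 6.5 expects a fall from about 35% to 20%, again framed as before to after.

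In section 6.4, treatment effects for the primary and secondary "outcomes related to receipt of all methods of contraception, we will use a generalized linear mixed model" with a random clinic effect and a fixed effect per time interval. Short IPI is not a contraception-receipt outcome. For outcomes in general, the same section says "they will plot rates of our outcomes over each" three-month period.

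Section 6.0 also says "A limitation of the stepped wedge design is the confounding effect of time", and to help with this "4 additional clusters will be randomized to either the control or the intervention for the entire study period". On numbers it says "We will include the 7 CHCs (six urban, one rural) recruited through Aim 1 of this project", yet it assigns one urban and one rural site to each step.

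**The concern.** The protocol names calendar time as a confounder and adjusts for it in the model for the contraception outcomes. It gives short IPI no model, test or time adjustment. A clinic's later rate against its own earlier rate mixes the intervention effect with whatever else changed over the period, and the baseline starts in April 2021. Reducing short-interval pregnancy is one of the two effects stated in the Aim 2 hypothesis (section 3.0), so a trend could produce or hide one of the trial's headline findings.

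**Working it through.** **Plan's own figure.** Section 6.5 anticipates 35 − 20 = 15 points. The documents give no secular trend, sample size or intracluster correlation for this outcome, so the sizes below are illustrations under stated assumptions.

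**Calendar inputs.** Control starts on 1 April 2021 and the first go-live is 1 August 2021, month 4 (sections 3.0 and 6.5). Steps are three months apart and there are 7 clinics (section 6.0). Clinics per step cannot be settled from the text, so two layouts are used, with go-live month s:
- one per step: 4, 7, 10, 13, 16, 19, 22 (mean 13)
- two per step: 4, 4, 7, 7, 10, 10, 13 (mean 55/7 = 7.86)

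**Drift.** The control period has its midpoint at s/2. The gap to a month-18 reading is s + 18 − s/2 = s/2 + 18. The gap to the middle of an 18-month window is s/2 + 9. Apparent change = drift per year × mean gap / 12.

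| Layout | Reading | Mean gap (months) | 1 point/year | 4 points/year |
|---|---|---|---|---|
| One per step | time point | 6.5 + 18 = 24.5 | 2.0 | 8.2 |
| One per step | window | 6.5 + 9 = 15.5 | 1.3 | 5.2 |
| Two per step | time point | 3.93 + 18 = 21.9 | 1.8 | 7.3 |
| Two per step | window | 3.93 + 9 = 12.9 | 1.1 | 4.3 |

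These changes arise with no intervention effect. A falling trend mimics benefit and a rising one hides it.

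**Can time adjustment be done?** With clinic and month effects, the intervention effect is estimable only if some calendar month holds both control and intervention data.
- Window: estimable in all six layouts checked (one or two clinics per step; no transition, or a three-month transition before or after go-live).
- Time point, two per step: the last control month is 12 and the earliest post reading is in month 19, so there is no overlap.
- Time point, one per step: the last clinic's control data run to month 21. A quarter starting at month 18 first falls in month 22, so there is no overlap. A quarter ending at month 18 first covers months 19 to 21, and one spanning it reaches month 21, so both overlap. If the three months before go-live are dropped as transition, control data end at month 18 and the overlap is lost.
- Of 18 time-point layouts (2 step sizes × 3 quarter placements × 3 transition rules), 4 are estimable from the 7 crossing clinics alone. With two always-control clusters observed throughout, all 18 are.

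**Build-up of the effect.** A short-interval patient presenting soon after go-live often delivered before it. Assume short intervals are spread evenly over 18 months and that presentation follows conception by 0 or 3 months. At t months after go-live, the share who delivered after go-live is max(0, t − lag)/18. Averaged over t = 0 to 18:
- lag 0: 9/18 = 0.500
- lag 3: (15²/2)/(18 × 18) = 0.347

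So 50% to 65% of short-interval patients counted as after go-live delivered before it. Some of these could still be reached, because "Women will be offered this co-scheduling option at each WBV through six months PP". If everyone who delivered up to six months before go-live counts as exposed, the shares become 0.778 and 0.653.

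For a gradual effect of this shape, the window reading and a linear model, one clinic per step gives:
- a single on/off term with interval effects recovers about −27% to 64% of the full effect, because early-switching clinics act as comparators while their own effect is still growing
- a build-up term with a compromise assumption (1.5-month lag, 3 months of pre-go-live exposure) recovers 69% to 104%, or 53% to 109% with two clinics per step
- the raw before/after change recovers 35% to 85%, but only if there is no drift

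**Precision.** The ratio of the time-adjusted on/off standard error to that of the raw change (no transition, before, after) is 1.89, 2.09, 2.20 with one clinic per step and 2.01, 2.34, 2.76 with two.

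**The case against.** The best reply is that time is not ignored. Section 6.4 plots the outcomes by quarter expressly to look at intervention and time effects, and section 6.3 has reports pulled monthly. Quarterly short IPI data may therefore already be intended, and collecting them would be partly a clarification. This stands, but a plot yields no adjusted estimate.

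A reader might go further and infer that the design cannot separate the short IPI effect from time. The documents do not support that. Under the window reading the effect is estimable in every layout checked. Under the time-point reading, failure in most layouts applies only to the 7 crossing clinics; section 6.0 provides for extra clusters held in one condition, and always-control clusters observed throughout would restore estimability. Calendar quarters fixed from 1 April would also make some time-point layouts nominally estimable, because the August start falls inside a quarter. What is missing is a specified analysis and a clear schedule. No limit of the design is established.

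The drift is assumed, and the build-up figures rest on assumed lags and evenly spread intervals. They show the size of the risk and do not predict it. No single build-up formula follows from the documents.

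**Conclusion.** The concern holds as a gap in the planned analysis. As written, short IPI is each clinic's after rate against its before rate, and the time-adjusted model does not cover it. The illustrated bias of about 1.8 to 8.2 points (time point) or 1.1 to 5.2 points (window) rests on an assumed drift of 1 to 4 points per year and on one or two clinics per step with no transition months dropped. At the upper end it exceeds half of the 15 points anticipated for the time-point reading (8.2/15 = 55%) and is about a third for the window (5.2/15 = 35%).

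It would be wrong to carry this over to the primary outcome: contraception receipt by two months, and by six months, has a model with interval effects. This should be fixed, but it does not threaten the main comparison.

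**What to change.** - **Section 6.4.** Extend the planned mixed model (random clinic effect, fixed interval effects) to short IPI among incoming prenatal patients. Let the intervention effect depend on time since go-live, for example through an exposure-share term rising over 18 months, because an on/off term alone would understate a gradual effect. State the assumed presentation lag and any assumed exposure of women who delivered before go-live, and vary both in sensitivity analyses. Report the on/off estimate as secondary.
- **Section 6.2.** State that short IPI is collected in every three-month interval through each clinic's control period and for the 18 months after go-live.
- **Section 6.0.** Reconcile the 4 additional clusters with the 7-clinic total, and the pairing of one urban with one rural site per step with a single rural clinic. State how many clinics switch per step, how transition months are handled, and whether any always-control clusters enter the short IPI analysis.

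**Cost.** The data source and population stay the same. If a month-18 reading was meant, the outcome widens from one reading to a series. Precision falls: the on/off standard error is about 1.9 to 2.8 times that of the raw change, and wider still with a build-up term. With 7 clinics the SAP should say that the short IPI estimate may be inconclusive.

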6.3 Data Collection

AllianceChicago's information technology (IT) team will build custom templates to match

PP women and their infant's records. They will create a study-specific field in the EHRS during WBV to prompt and record whether a co-scheduled appointment is **offered** to the mother. Similarly, a unique field will be created to record that a PP appointment is **co-scheduled** with a WBV appointment. The IT team will build custom reports in their data warehouse for the investigators to access and validate data in real-time. Reports will be built to pull data (ICD, CPT, and HCPCS codes) from the medical record and billing claims. In addition to real-time data, reports will be pulled monthly and reviewed closely by Drs. [name] and [name] and their investigative team. Findings from the reports will be used to determine the primary and secondary outcomes.

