6.5 Expected Outcomes

Intervention: After the intervention period begins, postpartum women within the selected CHC sites will be more likely to receive any contraceptive method by two and six months postpartum. We anticipate a minimum absolute increase in contraception use of 15% (from 45% to 60%) and a decrease in short IPI pregnancies from approximately 35% to 20% from before to after the intervention, both of which would have a clinically meaningful impact on the population.

Implementation Process: By the end of Aim 2, we expect the intervention will be implemented successfully at all sites. However, important clinic-level and system-level barriers will be identified at each site. For example, the discharge process likely occurs in slightly different ways in each clinic, which may impact who responds to the alert in the EHR and the efficiency in which the co-scheduling can be accomplished.

All modifications (i.e. custom fields, prompts) within EHR and scheduling software have been built. Participating CHC's have been randomized for the intervention. All sites entered the control period April 1, 2021 and the first site will enter the intervention period August 1, 2021.

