7.2 Data Collection

AllianceChicago's information technology (IT) team will build custom reports in their data warehouse to access and validate data in real-time. Reports will be built to pull data (ICD, CPT and HCPCS codes) from the medical record and billing claims; which will be used to determine implementation success. Reports will be built to monitor: 1) EHR alert consistency; 2) if co-scheduled care is offered; 3) if co-scheduled care is accepted or declined by women; 4) among those who accept, if both the co-scheduled appointments are completed

At approximately the midpoint of each site's intervention period, key informant interviews will be conducted with staff, physicians and PP women to assess implementation

outcomes such as acceptability, feasibility, and fidelity over time. Semi-structured interview guides will be developed around CFIR constructs (similar to Aim 1) to elicit information related to barriers and facilitators encountered during the implementation of linked care and the RE-AIM implementation outcomes listed in Table 3. Interviews will be audio-recorded and transcribed and carefully reviewed by both PIs. If the subject declines to have their interview recorded, they will be asked to complete the interview in person and notes will be taken in lieu of audio-recording.

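### Section 6.3 names only ICD, CPT and HCPCS codes for the any-contraception outcome and no medication orders, so methods prescribed to an outside pharmacy can be under-counted

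*Combined protocol and SAP*

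**What the plan says.** Section 6.2 names the primary outcome as "Receipt of all methods of contraception by two months PP". For its construction it says "we will create a dichotomous variable for receiving any contraception by two months PP", and it gives the source in general terms: "Using de-identified patient-level EHRS data for eligible women at each clinic within each time interval". The six-month secondary outcome is built the same way: "This outcome will be calculated similar to the primary outcome with the exception of time-period".

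Section 6.3 gives the only data elements named for the clinical outcomes: "Reports will be built to pull data (ICD, CPT, and HCPCS codes) from the medical record and billing claims". It then ties those reports to the endpoints: "Findings from the reports will be used to determine the primary and secondary outcomes". Section 7.2 repeats the same three code systems for the Aim 3 reports: "Reports will be built to pull data (ICD, CPT and HCPCS codes) from the medical record and billing claims".

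Section 6.5 anticipates a rise in contraception use from 45% to 60%. The Aim 2 text does not mention medication orders, prescriptions, medication lists or dispensing records, and no list of codes says what counts as receipt.

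**The concern.** The endpoint covers every method, but the named inputs do not record every method equally well. In general, ICD codes carry diagnoses and reasons for a visit, CPT codes carry procedures, and HCPCS codes carry supplies and drugs billed by the clinic. An implant or IUD placed, or an injection given, at the clinic leaves a procedure or supply code. A pill, patch or ring sent to an outside pharmacy need not leave any of the three. Its main way into the outcome is a contraception diagnosis code entered at the visit. Unless the plan says otherwise, such a code might also be entered when a woman was counselled and received nothing.

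Two things are at stake. If capture is incomplete to the same degree in both conditions, both rates and their difference shrink. If capture differs by condition, the estimate is biased in either direction. That could happen because a visit booked for contraception prompts more contraception coding, or because linked care changes the mix of clinic-placed and prescribed methods. The mixed model in section 6.4 adjusts for time and clinic. It cannot remove a capture difference that starts when the intervention starts.

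**Working it through.** **Text check.** The data-source statements, side by side:

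| Section | Source named | Medication data named? |
|---|---|---|
| 6.2, primary outcome | Patient-level EHR data, in general | No |
| 6.2, six-month outcome | As for the primary outcome | No |
| 6.3 | ICD, CPT and HCPCS codes, plus study fields for offered and co-scheduled visits | No |
| 7.1, Table 3 | EHR, in general | No |
| 7.2 | The same three code systems | No |

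**The plan's own figure.** The documents give no sample size or power calculation to reproduce. The anticipated effect is consistent: 60 - 45 = 15 points.

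**Illustration with equal capture.** Inputs:
- True rates of 45% and 60% (section 6.5, taken here as true rates).
- s = share of receipts that are prescription-only, assumed 0.3 to 0.5.
- c = share of those that carry a usable code, assumed 0.5 to 0.9.
- All other methods fully captured, no false positives, and the same s and c in both conditions.

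Overall capture = (1 - s) + s × c, and recorded rate = true rate × capture.

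| s | c | Capture | 45% recorded as | 60% recorded as | Difference (points) |
|---|---|---|---|---|---|
| 0.3 | 0.9 | 0.97 | 43.65% | 58.20% | 14.55 |
| 0.5 | 0.9 | 0.95 | 42.75% | 57.00% | 14.25 |
| 0.3 | 0.5 | 0.85 | 38.25% | 51.00% | 12.75 |
| 0.5 | 0.5 | 0.75 | 33.75% | 45.00% | 11.25 |

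The loss is between 15 - 14.55 = 0.45 and 15 - 11.25 = 3.75 points.

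**Illustration with unequal capture and no true effect (45% in both conditions).**
- *Coding changes.* Spurious difference = 45 × s × (c under intervention - c under control). With c rising from 0.5 to 0.9, this is 45 × 0.3 × 0.4 = 5.4 points at s = 0.3 and 45 × 0.5 × 0.4 = 9.0 points at s = 0.5.
- *Method mix changes.* With c = 0.5 throughout and s falling from 0.5 to 0.3, capture rises from 0.75 to 0.85. The recorded difference is 45 × (0.85 - 0.75) = +4.5 points. The reverse shift gives -4.5.

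These two cases show direction and order of magnitude only. The documents do not say that coding or method mix will change.

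**The case against.** The strongest reply is that the list in 6.3 need not be complete. The same section creates fields for offered and co-scheduled visits. The reports in 7.2 track alert consistency, offers, acceptance or refusal, and completed appointments. None of these is an ICD, CPT or HCPCS code, so the reports plainly carry other data. Section 6.2 and Table 3 name the health record in general. This stands in part: a reader might infer that the plan excludes prescribed methods, and the documents do not show that. They show that the only elements named for the outcome do not include medication data, and nothing elsewhere adds them.

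Three other stronger readings also go too far:
- *Prescribed methods count only through a diagnosis code.* A pill, patch or ring dispensed and billed by the clinic could carry a supply code. The gap concerns outside-pharmacy prescriptions.
- *The outcome becomes largely a measure of clinic procedures.* Under the assumptions above, overall capture is 75-97%. Prescribed methods make up s × c / capture of recorded receipts, from 0.15/0.85 = 18% (s = 0.3, c = 0.5) to 0.45/0.95 = 47% (s = 0.5, c = 0.9).
- *Counselling-only codes will be counted as receipt.* With no code list, the plan does not settle this either way.

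The size is also open to challenge. Both s and c are assumed. Equal under-capture pulls the effect toward zero, which is conservative, and at the favourable end the loss is negligible. Section 6.5 does not say whether 45% and 60% are true or record-based rates. If they are record-based, some under-capture is already in them and the computed shrinkage does not apply. Finally, that the warehouse holds medication orders is a reasonable inference, not a stated fact.

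**Conclusion.** The point holds as a gap in a stated measurement rule. The reports that decide the primary and six-month outcomes are specified by three code systems that do not reliably record a prescription filled elsewhere, and receipt is not defined. Followed as written, the pull can under-count short-acting methods.

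On the stated assumptions (30-50% prescription-only, 50-90% of those coded, equal capture, 45% and 60% as true rates), the 15-point effect would be recorded as about 11 to 14.5 points. None of the capture inputs comes from the documents, so this is a range of consequences and not an estimate. Unequal capture is the more serious possibility because it can create or hide an effect, but it remains a possibility. The plan should be changed. If medication orders were always intended, the source can be named in one sentence, but the definition of receipt would still be needed.

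**What to change.** Change sections 6.2 and 6.3:

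1. Add contraceptive medication orders from the mother's record to the outcome pull, where the warehouse holds them.
2. Define receipt as a procedure or supply code, or a contraceptive medication order, dated from delivery to the two- or six-month cut-off.
3. State that a diagnosis code for counselling alone is not receipt.
4. Apply the definition identically to control and intervention periods, including control data from April 2021 onward.
5. Tabulate receipt by source (procedure or supply, medication order) and by condition, so that a difference in capture can be seen.

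Section 7.2 needs no change on this account: the four items it monitors do not use medication data.

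The cost is one additional data element, subject to confirming that the warehouse can supply it. An order does not prove that the method was dispensed, and the plan should say so.

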The current standard of care is to address women's PP contraceptive needs at the six-week PP visit. However, this model of care is ineffective for many reasons, particularly for low-income women. First, many women resume sexual intercourse before six-weeks PP and prior to initiation of contraception.^{20,21} Second, many women do not attend the six-week PP visit.²² Prior analyses of Illinois Medicaid data by our team, and an analysis of California Medi-Cal data, found PP visit rates to be 56% and 49.4% (respectively).^{22,23} In addition, health disparities exist resulting in African-American women and women living in high poverty communities experiencing the lowest rates of PP care.²² Third, few women who return for PP care receive contraception at this time due to a provider barrier (i.e., inadequate time to address contraception at the visit, less skilled providers with lack of knowledge about medically appropriate PP contraception or requiring return visit for placement of long-acting methods).¹¹ Fourth, the timing of the six-week PP visit is based on tradition rather than evidence supporting improved patient outcomes.^{24,25} Finally, efforts to date such as antenatal discussion of the importance of the PP visit, use of discharge planners to encourage PP follow-up, and email and text reminders have had limited impact on increasing attendance at PP visits or contraception use.^{26,27} This has led to testing alternative strategies to improve uptake of PP contraception, such as providing contraception prior to hospital discharge after delivery.^{28,29} Unfortunately, efforts to increase immediate PP contraception provision have also faced significant implementation challenges due to lack of knowledge among providers of appropriate immediate PP contraception options, financial concerns regarding billing and reimbursement, and competing clinical and administrative priorities.³⁰ **Thus, there is an urgent need for new approaches to improve timely access to contraception for PP women.**

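### Linked care may raise the chance that contraception obtained elsewhere is coded at the health centre, so part of the recorded effect may not be a change in women's use

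*Combined protocol and SAP*

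**What the plan says.** **Source of the outcome.** Section 6.0 says that "outcomes may be obtained through routinely collected de-identified data from the common AllianceChicago EHR". Section 6.2 defines the primary outcome as "Receipt of all methods of contraception by two months PP". It takes this from patient-level records at each clinic and reduces them to a yes/no measure: "we will create a dichotomous variable for receiving any contraception by two months PP". Section 6.3 gives the route: "Reports will be built to pull data (ICD, CPT, and HCPCS codes) from the medical record and billing claims". It adds: "Findings from the reports will be used to determine the primary and secondary outcomes". Table 3 in section 7.1 also names the EHR as the source for effectiveness. The six-month outcome is built the same way.

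**What the intervention does.** Under section 6.0, an electronic prompt leads staff to offer the mother a contraception visit alongside the infant's next visit. The offer is repeated at well-baby visits (WBVs) through six months.

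**How the result is labelled.** Section 3.0 (Aim 2) speaks of clinic-level provision. Section 6.2 speaks of receipt. Section 1.0 speaks of women using contraception. Section 6.5 also puts the expected effect as use: "We anticipate a minimum absolute increase in contraception use of 15% (from 45% to 60" per cent).

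**What is not stated.** The plan gives no contraception code list, no rule for a woman with no maternal record, no check of the coded outcome against an independent source, and no sensitivity analysis for capture. Real-time validation in section 6.3 concerns the investigators' access to the reports.

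**The concern.** The outcome is observed through maternal contact with the CHC, and the intervention is designed to increase that contact. The plan itself notes that contraception can come from elsewhere: section 2.0 mentions strategies such as "providing contraception prior to hospital discharge after delivery". Inclusion (section 6.1.1) depends on the infant's first visit, so some women in the denominator may obtain a method outside the centre. If such a method is coded only when the mother has a CHC encounter, it may appear more often after a site switches, although her use has not changed.

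Section 6.4 adjusts for site (random effect) and time interval (fixed effect). A change in coding that begins when a site switches coincides with the intervention indicator, so neither term absorbs it. Randomising the order of switching does not help either. Short inter-pregnancy interval is not an independent check, because section 6.2 also takes it from the centres' records.

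At stake is what a positive result means: more women using contraception, or more contraception supplied or recorded at the CHC.

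**Working it through.** **1. The plan's own figure.** 60% − 45% = 15 percentage points, as section 6.5 says. No sample size, power or alpha is given for Aim 2, so there is nothing further to reproduce.

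**2. Size of the artefact with true use unchanged.** Let p be the share of all women with an outside method in the window. Let d1 and d0 be the shares of those women whose method is documented at the CHC under linked and usual care. Then

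spurious points = p × (d1 − d0).

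Only the increment d1 − d0 counts, because usual care also documents some outside methods. The documents give none of these inputs. The ranges below are assumptions.

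| p | d1 − d0 | Spurious points | Share of 15 |
|---|---|---|---|
| 5% | 25 points | 1.25 | 8% |
| 5% | 50 points | 2.5 | 17% |
| 20% | 25 points | 5 | 33% |
| 20% | 50 points | 10 | 67% |

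**3. Effect of documentation under usual care.** Take p = 20% and d1 = 50%. With d0 = 0 the artefact is 20% × 50 = 10 points. With d0 = 25% it is 20% × (50 − 25) = 5 points.

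**4. Cross-check through visit rates.** Suppose a share s of true uptake T is obtained elsewhere and is coded only if the mother has a CHC visit, with visit rate v0 under usual care and v1 under linked care. The recorded rate is T × [(1 − s) + s × v], so the spurious rise is T × s × (v1 − v0). For v0, section 2.0 cites postpartum visit rates of 49.4% and 56%; these come from California Medi-Cal and Illinois Medicaid analyses, not from these centres. Assume T = 50% to 70%, s = 10% to 40% and v1 = 65% to 90%.

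- Low end: 0.50 × 0.10 × (0.65 − 0.494) = 0.8 points, 5% of 15.
- High end: 0.70 × 0.40 × (0.90 − 0.56) = 9.5 points, 63% of 15.

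This agrees with the range in step 2.

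**5. What it would take to produce all 15 points.** At p = 20% the increment would have to be 15/0.20 = 75 points. At an increment of 50 points, p would have to be 15/0.50 = 30%. Both lie outside the ranges in step 2.

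**The case against.** Several parts of the plan limit the bias, and they stand.

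- The prompt in section 6.0 reaches established patients only. For mothers who are not CHC patients, it should not change detection.
- Section 6.0 lets women who do not need care decline. Those who already have a method are plausibly the likeliest to do so.
- Section 6.0 excludes women with planned immediate long-acting contraception, which removes an obvious group with a hospital-placed method. Section 6.1.2 does not list this exclusion, so the two must be reconciled. The omission does not show that these women stay in the analysis.
- Section 2.0 says that few women receive contraception before the six-week visit and that immediate postpartum provision has been hard to implement. Both give reason to doubt the top of the assumed 5% to 20%.
- The plan does not say whose billing claims are used. Payer claims would capture some outside care.
- If the target is clinic-level provision, as in section 3.0, a move of provision to the CHC is a real effect. A refill by the CHC is also actual provision.

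A reader might infer that the whole planned effect could be an artefact, since a one-third rise in capture (0.60/0.45 = 1.33) would reproduce it with no change in use. The documents give no capture figures to support that. Nor do they say that every woman with an outside method is scored as a failure under usual care, or that linked care brings all of them to a visit.

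These points reduce the likely size. They do not remove the dependence of detection on condition, or the mismatch between provision and use.

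**Conclusion.** The concern holds in a limited form. The contraception outcomes rest on CHC records and billing codes, the intervention adds encounters that generate such records, and the planned model cannot separate added recording from added contraception. The direction would favour linked care. The extra encounters are the intended mechanism, not a figure in the documents, and part of any recorded rise would be genuine new provision.

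The size is not derivable from the documents. Under the assumed inputs it is about 1 to 10 points against the planned 15, and smaller the more usual care already documents. The point affects what the trial can conclude: the planned data can support a statement about contraception provided or recorded at the CHC, but not by themselves one about women's use.

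**What to change.** 1. **One code list, pre-specified and applied in both conditions.** Separate methods prescribed, dispensed or placed by the CHC after the first WBV from surveillance or history codes. Report the effect on CHC provision alone beside the all-codes result, and state whether the billing claims include payer claims. This deals with newly documented methods. It does not deal with a woman who now starts at the CHC a method she would have started elsewhere, and a CHC refill of an outside method may still count as provision.
2. **Encounter share.** Report by condition the share of women with no maternal CHC encounter in the two- and six-month windows, and state how they are classified. Section 7.2 already monitors completion of co-scheduled visits; the usual-care side needs the same count from encounter data.
3. **Wording.** Reconcile sections 1.0, 3.0, 6.2 and 6.5, and state the outcome and conclusion as contraception provided or recorded at the CHC. This covers the shift of source that the code split leaves in. Reconcile sections 6.0 and 6.1.2 on planned immediate long-acting contraception.

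The cost is code-list work, one more analysis and a narrower claim. No new data collection is needed.
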